5.5 Pharmacokinetic, Pharmacodynamic, Pharmacogenomic, and Other Biomarker Analyses

5.5.1 Pharmacokinetic Analyses

The Safety Analysis Set will be used for individual perampanel plasma concentration listings and summaries of perampanel plasma concentrations. Plasma perampanel concentration data at Early transition visit or Early discontinuation visit will not be included in tables and figures for pharmacokinetic analysis. The plasma perampanel concentration data will be excluded from the plasma concentration analysis if the treatment compliance during site visits at Visit 4, 5, 7, 4a, 5a, or 7a where PK blood sampling will be conducted is inadequate for PK evaluation including following cases but not limited to:

- The dose amount is not constant during the last 3 doses of perampanel before PK blood sampling at Visit 4, 5, 7, 4a, 5a, or 7a.
- The perampanel is not administered on consecutive 3 days just before PK blood sampling at Visit 4, 5, 7, 4a, 5a, or 7a.
- Treatment compliance rate during site visits before PK blood sampling at Visit 4, 5, 7, 4a, 5a, or 7a is <80%.

5.5.1.1 Plasma Concentration Analysis

<Concentration>

Plasma concentrations for perampanel will be summarized using summary statistics (n, mean, SD, median, min and max) at the 4 mg Treatment Phase and at the 8 mg Treatment Phase, respectively, by actual dose of the Treatment Phase for all subjects.

Plasma concentrations for perampanel will be summarized using summary statistics (n, mean, SD, median, min and max) at the 4 mg Treatment Phase and at the 8 mg Treatment Phase, respectively, by actual dose of the Treatment Phase for patients who have at least one plasma perampanel concentration data at the 8 mg Treatment Phase (Titration Period and Maintenance Period).

Plasma concentrations of perampanel will be listed for each subject by actual sampling time.

The relationship between plasma concentrations of perampanel at steady state and seizure free status will be analyzed graphically.

- Individual plasma concentrations of perampanel will be displayed by seizure-free status of the 26-week Maintenance Period at week 6 of the Titration Period of 4 mg (Visit 4) and at week 4 of the Titration Period of 8 mg (Visit 4a).
- Last plasma concentrations of perampanel of 4 mg Treatment Phase and 8 mg Treatment Phase will be displayed individually in subjects who have at least 1 each plasma perampanel concentration data of both the Treatment Phase of 4 mg and 8 mg.

5.5.2 Pharmacodynamic, Pharmacogenomic, and Other Biomarker Analyses

Not applicable

5.6 Safety Analyses

All safety analysis will be performed based on the Safety Analysis Set. Safety data will be summarized using descriptive statistics (e.g., n, mean, standard deviation, median, minimum, maximum for continuous variables; number [percentage] for categorical variables). The analysis window for summarizing the safety parameters by visit will be defined in the [section 8.3](#). The follow-up Phase will not be included in the by visit summary tables, unless otherwise indicates.

5.6.1 Extent of Exposure

The parameters for extent of exposure defined as follows will be summarized for the period of the entire study (treatment phase or the extension phase). Here “dose” is not actual dose but planned dose. Duration of exposure, last dose and mean daily dose will also be performed for the period of treatment phase.

1. Duration of exposure (weeks)
 - From the date of first study drug dosing to the date of last study drug dosing including the Follow-up Phase
2. Maximum dose
 - From the date of first study drug dosing to the date of last study drug dosing not including the Follow-up Phase
3. Last dose
 - From the date of first study drug dosing to the date of last study drug dosing not including the Follow-up Phase
4. Mean daily dose
 - From the date of first study drug dosing to the date of last study drug dosing not including the Follow-up Phase
5. Number of subject-weeks
 - Summation over all subject’s exposure durations

Duration of exposure to the study drug for the period of the entire study will be classified by categories of cumulative weeks (ie, > 6 weeks, > 14 weeks, > 26weeks, > 38 weeks, > 52 weeks, > 64 weeks, > 76 weeks, 12-week interval thereafter). The number (percentage) of subjects in each category will also be summarized.

Subject data listings will be provided.

5.6.2 Adverse Events

The AE verbatim descriptions (investigator terms from the CRF) will be classified into standardized medical terminology using the Medical Dictionary for Regulatory Activities (MedDRA version 19.0 or later). Adverse events will be coded to the MedDRA lower level term (LLT) closest to the verbatim term. The linked MedDRA preferred term (PT) and primary system organ class (SOC) will also be captured in the database.

A treatment-emergent adverse event (TEAE), defined in “8.3 Safety Data Handling”, will be included in summary tables. All AEs, treatment emergent or otherwise, will be presented in subject data listings.

A subject will be counted only once within a SOC and PT, even if the subject experienced more than 1 TEAE within a specific SOC and PT.

An overview table, including the incidence of and the number of subjects with TEAEs, Treatment-related TEAEs, severe adverse event, serious adverse events (SAEs), deaths, and TEAEs that led to treatment discontinuation, dose reduction and interruption will be provided.

All analysis of TEAEs by SOC and PT will also be performed for the Treatment Phase and the entire study period (ie, the Treatment Phase or the Extension Phase). The incidence of below events will be reported as the number (percentage) of subjects with TEAEs by MedDRA SOC and PT.

- TEAEs
- TEAEs by maximum severity
- Serious TEAEs
- Non-serious TEAEs
- Treatment-related TEAEs
- Treatment-related TEAEs by maximum severity
- Treatment-related serious TEAEs
- Treatment-related non-serious TEAEs
- TEAEs leading to discontinuation
- TEAEs leading to dose reduction
- TEAEs leading to interruption

In addition, The analysis of TEAEs by SOC and PT will also be performed by dose. The analysis by period will be summarized every 3 months, but a subject will be counted only the first once within a PT throughout the entire period, even if the subject also experienced TEAE in other later period. The analysis by dose will be summarized using final dose for the Treatment Phase and dose at or prior to AE onset dose for the entire study period.

Subject data listings of all deaths, SAEs, AEs leading to death, treatment discontinuation, dose reduction and interruption will be provided. All AE regardless of treatment-emergent or not will be included in the subject data listings.

AEs of special Interest

The following categories of TEAEs of special interest will be summarized by PT.

TEAEs related to suicidality

TEAEs suggestive of abuse potential
 TEAEs related to alertness and cognition
 TEAEs related to psychosis / psychotic disorders
 TEAEs related to hostility/aggression
 TEAEs related to status epilepticus/convulsions
 TEAEs related to drug-related hepatic disorder abnormalities
 Cardiac and ECG TEAEs

A Standardized MedDRA Query (SMQ) will be used to identify relevant terms for each category of TEAEs of special interest.

Name of AEI	SMQ to be used	Range
TEAEs related to suicidality	SMQ for depression and suicide/self-injury	Narrow
TEAEs suggestive of abuse potential	SMQ for drug abuse, dependence and withdrawal	Narrow and Broad Narrow
TEAEs related to alertness and cognition	SMQ for dementia	Narrow and Broad
TEAEs related to psychosis/psychotic disorders	SMQ for psychosis and psychotic disorders	Narrow and Broad Narrow
TEAEs related to hostility/aggression	SMQ for hostility/aggression	Narrow and Broad Narrow
TEAEs related to status epilepticus/convulsions	SMQ for convulsions	Narrow and Broad
TEAEs related to drug-related hepatic disorder abnormalities	SMQ for drug-related hepatic disorders-comprehensive search	Narrow and Broad
Cardiac and ECG TEAEs	SMQs for cardiac arrhythmia terms (including bradyarrhythmias and tachyarrhythmias), arrhythmia related investigations, signs and symptoms; cardiac failure; cardiomyopathy; ischaemic heart disease; and Torsade de pointes/QT prolongation	Narrow and Broad

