## 9.2 Discussion of Study Design, Including Choice of Control Groups

This study is a multicenter, open-label study to evaluate the efficacy, safety and tolerability, and pharmacokinetics of perampanel.

During initial treatment, the dose of monotherapy should be gradually increased to a therapeutic range based on the subject's safety and tolerability (Matsuura, 2009). The interval of titration for each dose was 1 week in the studies of adjunctive therapy, while it is changed to 2 weeks in this study. The point to be considered in medication is the following report (Matsuura, 2009): "When unfavorable side effects such as sleepiness occur in a subject, transient reduction to the dose before titration and re-up-titration to planned dose can make the planned dose administered to the subject." Based on the above report, dose reduction from 4 mg to 2 mg is allowed during the 4 mg Titration Period.

The 26-week Maintenance Period is the duration to evaluate the seizure-free rate as primary objective (see Section 7.2). In addition, the Extension Phase is established to confirm the subsequent seizure-free period for subjects who completed the Maintenance Period; and the subsequent clinical course of non-seizure-free subjects who do not have trouble in daily life, have sufficient therapeutic effect, and desire to continue the study. If subjects need to take other AEDs because of insufficient efficacy of perampanel, they will discontinue the study.

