## 24. Subject who is diagnosed with dementia

### 9.3.3 Removal of Subjects From Therapy or Assessment

The investigator may withdraw the subject from the study at any time for safety or administrative reasons. The subject may stop study drug or withdraw from the study at any time for any reason.

A subject who discontinues study treatment should be followed for subsequent protocol-specified visits and procedures. The primary reason for discontinuation contributing to the subject's discontinuation from study drug(s) should be collected. If subjects need to take other AEDs because of insufficient efficacy of perampanel, they will discontinue the study. The first date when other AEDs are administered will be defined as the final date of perampanel monotherapy, and the subsequent date when the perampanel is completely withdrawn will be defined as the discontinuation date of the study.

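### The alertness and cognition special-interest category is searched only with a dementia query and can under-report alertness events; the suicidality category uses a query that also covers depression

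*SAP*

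**What the plan says.** SAP 5.6.2 lists eight special-interest categories, to be summarized by preferred term (PT), and states one search tool for all of them: "A Standardized MedDRA Query (SMQ) will be used to identify relevant terms for each category of TEAEs of special interest". A table then gives the query and its range for each category. Two rows matter here.

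- "TEAEs related to alertness and cognition" is mapped to "SMQ for dementia", with narrow and broad range.
- "TEAEs related to suicidality" is mapped to "SMQ for depression and suicide/self-injury", with narrow range.

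The SAP gives no reason for either mapping, no supplementary term list, and no separate line for suicide and self-injury alone. SAP section 7 records the special-interest summaries among the minor additions to the protocol's analyses.

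Protocol 9.2 quotes a published report that begins "When unfavorable side effects such as sleepiness occur in a subject", and uses it to support the dose reduction permitted during the 4 mg Titration Period. Exclusion criterion 24 reads "Subject who is diagnosed with dementia".

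**The concern.** A special-interest category is useful because it gathers related terms that the general tables leave scattered. That works only if the search retrieves what the label promises. Here the label promises alertness and cognition, while the search is named for a different condition and nothing in its name points to alertness. A low count could then be read as reassurance about alertness when the search did not look for it.

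The suicidality row has a milder problem in the other direction: its query covers more than its label, so a count under that heading need not mean suicidal ideation or self-injury.

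Safety and tolerability is a secondary objective, and protocol 7.2 plans a comparison of safety data with Study 335 to evaluate safety signals. Schedule Tables 3 to 5 contain no suicidality scale and no cognitive or alertness test, and SAP 5.6.6 plans no other safety analysis. These two rows are therefore the only targeted summaries of their topics.

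**Working it through.** The plan states no figure on this point, so there is none to reproduce. The check compares labels with queries, followed by an illustration on assumed rates.

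**Label against query (SAP 5.6.2 table)**

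| Category | Query | Match by name |
|---|---|---|
| Alertness and cognition | Dementia, narrow and broad | Alertness: none. Cognition: related at most. |
| Suicidality | Depression and suicide/self-injury, narrow | Covers the label, and depression as well |

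In each of the other six rows the query name repeats the subject of the label. Alertness and cognition is the only row where it does not.

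**Does display by PT cure it?** For suicidality it does in part: a depression TEAE appears under its own PT and can be recognised. For alertness it does not, because a term that the query does not retrieve never enters the category table.

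**Size of a possible miss (alertness).** N = 80 comes from protocol 9.3. The sleepiness rate r is an assumption, 10% to 20%.

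- If the query retrieves no sleepiness term, the number missed is N × r: 80 × 0.10 = 8, up to 80 × 0.20 = 16 subjects.
- If it retrieves all of them, the number missed is 0.
- The range is therefore 0 to 16 of 80. The documents cannot narrow it, because the query's terms are not given.

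**Size of possible over-counting (suicidality).** N = 80. The rates for suicidality (s) and depression (d) are assumptions, with no subject having both. The expected count is N × s for the label alone and N × (s + d) for the query. The chance of at least one depression TEAE is 1 − (1 − d)^80.

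| s | d | Label alone | Query | Ratio | Chance of at least one depression TEAE |
|---|---|---|---|---|---|
| 1% | 0% | 0.8 | 0.8 | 1 | 0% |
| 1% | 1% | 0.8 | 1.6 | 2 | 55% |
| 1% | 2% | 0.8 | 2.4 | 3 | 80% |
| 1% | 5% | 0.8 | 4.8 | 6 | 98% |

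With s = 2% and d from 0% to 5%, the ratio runs from 1 to 3.5. The relative effect can be large, but it is a matter of a few subjects, and it is zero if no depression TEAE occurs.

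**The case against.** The strongest reply is that nothing is hidden. Under SAP 5.6.2 every TEAE is tabulated by system organ class and PT, also by maximum severity, by relationship to treatment, by whether it led to discontinuation, dose reduction or interruption, and by dose; all AEs are listed. Common sleepiness would be plain in those tables. This stands, and it confines the point to the special-interest summaries. It does not remove the point, since the general tables do not group related terms.

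A second reply is that the dementia query is run with its broad range, which may contain alertness terms. That is possible, and it is why the range starts at 0. A reader might infer that sleepiness events will be missed; the documents show only that they can be.

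Third, the suicidality query does name suicide and self-injury and is limited to the narrow range. The SAP specifies display by PT and no pooled category count, and the table shells are in a separate document. A reader might infer that this query is aimed at something else, or that the category is inflated as a matter of fact. Neither is supported: the query is broader than its label, and over-counting needs both a category-level count and depression TEAEs.

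Two further inferences fail. Sleepiness is not given as the reason for slow titration; protocol 9.2 ties it to the permitted dose reduction and offers it as an example. The exclusion of dementia does not show that the query will come back empty, because the criterion concerns diagnosis at entry while the query looks for treatment-emergent terms.

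Finally, replacing a standard query with a sponsor's own list in an open-label study would trade standardization for discretion, and could cost comparability with Study 335 if that study used the same searches. This is a fair argument against replacement, and the reason to add to the query and not remove it.

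**Conclusion.** The point holds in limited form. The alertness and cognition category rests on one query whose name does not cover alertness, with no rationale and no other term list, so it can under-report the kind of effect that the protocol itself uses as an example. The extent is unknown: the 0 to 16 of 80 rests wholly on the assumed sleepiness rate and on query content that the documents do not give.

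The suicidality part is secondary. The row is wider than its label, and the by-PT display goes most of the way to resolving that.

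Overall safety capture, the primary and secondary efficacy analyses and the sample size are untouched. Priority is minor to moderate.

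**What to change.** In the SAP 5.6.2 table:

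1. For alertness and cognition, keep the dementia query for continuity and add a PT list, fixed before database lock, for alertness (somnolence, sedation, lethargy and similar). Show alertness separately from cognition.
2. For suicidality, either show suicide/self-injury terms and depression terms under separate subheadings, or rename the row so that it states both depression and suicide/self-injury.

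The cost is a short PT list, a few lines of SAP text, and a footnote wherever the categories differ from earlier perampanel tables. No new data are needed and trial conduct does not change. Fixing the list before lock limits the discretion that an open-label study would otherwise leave to the sponsor.

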5.6.3 Laboratory Values

Laboratory results will be summarized using Système International (SI) units. For all quantitative parameters, the actual value and the change from baseline to end of treatment will be summarized using summary statistics. Qualitative parameters will be summarized by number and percentage of subjects, and changes from baseline to end of treatment will be reported using shift tables. Percentages will be based on the number of subjects with both nonmissing baseline and relevant postbaseline results.

Laboratory test results will be assigned a low/normal/high (LNH) classification according to whether the value is below (L), within (N), or above (H) the laboratory parameter's reference range. The result of LNH classification will be provided in a subject data listing.

“Sponsor’s Grading for Laboratory Values” will be used to identify subjects with Treatment-emergent markedly abnormal laboratory value (TEMAV). The number

(percentage) of subjects with TEMAV (markedly abnormal high/low) will be summarized for overall study period including the Follow-up Phase. The TEMAV will be defined in the [section 8.3](#). TEMAV will also be summarized for the Treatment Phase and the entire study period.

The baseline and end of treatment values for quantitative data will be displayed using Box plot.

Subject data listings will be provided.

5.6.4 Vital Signs

Summary statistics for vital signs parameters (diastolic and systolic blood pressure, pulse, Respiratory rate, and temperature) and weight, and changes from baseline to end of treatment will be presented.

The baseline and end of treatment values will be displayed using Box plot.

Subject data listings will be provided.

5.6.5 Electrocardiograms

Shift tables will present changes from baseline to end of treatment in ECG interpretation (categorized as normal; abnormal, not clinically significant; and abnormal, clinically significant).

Subject data listings will be provided.

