### 3. Safety Analyses

All safety analyses will be performed based on the Safety Analysis Set.

The AE verbatim descriptions (investigator terms from the CRF) will be coded to system organ class (SOC) and preferred terms (PT) using the Medical Dictionary for Regulatory Activities (MedDRA). The number (percentage) of subjects with treatment-emergent adverse events (TEAEs) and serious adverse events (SAEs) will be summarized by MedDRA SOC and PT. The incidence of TEAEs will be summarized by severity (mild, moderate, or severe). The TEAEs will be summarized for the Treatment Phase and the entire study period (ie, the Treatment Phase or the Extension Phase). The changes from baseline will be summarized by visit using descriptive statistics for continuous variables (eg, laboratory values, vital sign, weight, and ECG parameter). Categorical variables will be summarized as number (percentage) of subjects by visit.

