8.1 General Data Handling

Definition of Baseline data

Baseline is defined as the last non-missing value observed on or prior to the first study drug dispensing date.

Definition of Change from Baseline, Percent Change from Baseline

- Change from baseline = Post-baseline value - Baseline value
- % Change from baseline = (Change from baseline / Baseline value) * 100

For any baseline value of 0, the subject’s corresponding percent change from baseline will not be included in the summary statistics table.

Handling of data not within specified periods or within the follow-up period

Data obtained in the Follow-up Phase except for AE, Duration of Exposure and TEMAV will not be included in the summary tables. These data will be presented in the subject data listing.

Definition of End of Treatment

End of treatment phase during the 26-week Maintenance Period of the last evaluated dose is defined as the closest value observed on or post to the disposition date in the 26-week Maintenance Period of the last evaluated dose. If there is no adequate data, the closest value observed prior to the disposition date is selected.

End of treatment during the entire study (treatment phase or extension phase) is defined as the closest value observed on or post to the last disposition date in the entire study. If there is no data, the closest value observed prior to the last disposition date is selected.

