8.3 Safety Data Handling

Definition of derived variables for extent of exposure

The derivation rule will be presented in the [section 5.6.1](#).

Treatment-emergent adverse event

A treatment-emergent adverse event (TEAE) is defined as an AE that emerges during time from the first dose of study drug to the last visit or 28 days after the subject's last dose, whichever comes later, having been absent at pretreatment (Baseline) or

- Reemerges during treatment, having been present at pretreatment (Baseline) but stopped before treatment, or
- Worsens in severity during treatment relative to the pretreatment state, when the AE is continuous.

TEMAV (Treatment-Emergent Markedly Abnormal Value)

A TEMAV is defined as follows:

- For a phosphate, if the post baseline grade increases from baseline and the post baseline grade is greater than or equal to 3 then a value will be determined to be a TEMAV.
- For all other parameters presented in the [section 13.1](#), if the post baseline grade increases from baseline and the post baseline grade is greater than or equal to 2 then a value will be determined to be a TEMAV.

If the grade of baseline value is missing, then, if the grade of post-baseline value is Grade 2 or higher, the laboratory values will be classified into treatment emergent markedly abnormal.

Laboratory values, Vital signs, ECGs

For the end of treatment, the closest value measured on or post to the last disposition date in the Treatment Phase and the entire study period will be imputed using Last Observation Carried Forward (LOCF) method. If there is no adequate data, the closest value observed prior to the disposition date is selected.

Handling of below lower quantification values in laboratory results

In the cases where laboratory result contains below lower quantification (BLQ) value, it will be replaced to the lower limit value of quantification (LLOQ) for summary tables.

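### Vital signs and ECG interpretation are tabulated only at end of treatment, and the end-of-treatment rule looks forward before it looks back

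*SAP*

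**What the plan says.** **Protocol.** The synopsis, under safety analyses, plans: "The changes from baseline will be summarized by visit using descriptive statistics for continuous variables (eg, laboratory values, vital sign, weight, and ECG parameter". Section 9.7.1.8.4 plans vital signs and weight by visit, and section 9.7.1.8.5 plans shift tables of ECG interpretation by visit.

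**SAP tables.** For vital signs and weight, section 5.6.4 says that "changes from baseline to end of treatment will be presented", with box plots at the same two points. For ECGs, section 5.6.5 says: "Shift tables will present changes from baseline to end of treatment in ECG interpretation". Section 7 lists both departures from by-visit reporting among its minor changes and gives no reason. Section 5.6 nevertheless says: "The analysis window for summarizing the safety parameters by visit will be defined" in section 8.3, and it excludes the Follow-up Phase from by-visit tables.

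**SAP end-of-treatment rule.** Section 8.3 takes "the closest value measured on or post to the last disposition date in the Treatment Phase and the entire study period", calls this LOCF, and turns to an earlier value only when there is no adequate later one. Section 8.1 gives the same order for the whole study: "the closest value observed on or post to the last disposition date in the entire study". It also limits what may enter the tables: "Data obtained in the Follow-up Phase except for AE, Duration of Exposure and TEMAV will not be included in the summary tables".

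**The concern.** There are two separate problems.

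The first is coverage. Vital signs and ECGs are collected at several visits on treatment, but the planned tables of measured values use only baseline and end of treatment. A shift that appears mid-period and has gone by the end is not visible in those tables. Laboratory values lose their by-visit tables too, but they keep the table of treatment-emergent markedly abnormal values, which covers any post-baseline visit. Vital signs and ECGs have no counterpart.

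The second is the rule that selects the one value used. A rule that prefers later values, with no limit on how much later, can place a value from the Extension Phase in the Treatment Phase table.

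Safety and tolerability are a secondary objective of an uncontrolled study, and protocol 7.2 says the safety data will be compared with those of the adjunctive Study 335 to evaluate signals. End-of-treatment values pooled over different doses and lengths of exposure say little about when a measured change began or at what dose.

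**Working it through.** The plan gives no figure to reproduce here. The check compares sections and counts scheduled visits.

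**1. Planned tables of measured values**

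| Variable | Protocol | SAP | Any-visit abnormality table in SAP |
|---|---|---|---|
| Laboratory values | by visit (9.7.1.8.3) | end of treatment (5.6.3) | yes, TEMAV |
| Vital signs, weight | by visit (9.7.1.8.4) | end of treatment (5.6.4) | none |
| ECG interpretation | by visit (9.7.1.8.5) | end of treatment (5.6.5) | none |
| ECG parameters | by visit (synopsis only) | none | none |

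SAP 5.6.6 and 5.7 plan nothing further. Section 7 covers the first three rows but does not mention the fourth.

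**2. By-visit windows.** SAP 5.6 sends the reader to 8.3. Section 8.3 covers exposure, TEAEs, TEMAVs, the end-of-treatment rule and values below quantification. It contains no visit windows, and 5.6.3 to 5.6.5 plan no by-visit table that would use them.

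**3. Visits used (protocol Tables 3 and 4)**

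- 4 mg completer: post-baseline ECG and vital signs are scheduled at Visit 4 (Day 43), Visit 7 (Day 141) and Visit 9 (Day 225), which makes 3.
- Used in the Treatment Phase table: 1. Not used: 3 − 1 = 2 (Visits 4 and 7).
- 8 mg phase: assessments are scheduled at Visits 2a, 4a, 7a and 9a, and again one feeds the table. The 4 mg visits that came before depend on when the seizure occurred, so the 4 mg completer is the cleaner measure.

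**4. The rule applied to a missing Visit 9 value.** Assume that Extension Day 1 is the day of Visit 9 (Day 225) and that no unscheduled value exists.

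- Nearest earlier value, Visit 7: 225 − 141 = 84 days = 12 weeks before.
- Nearest later value, Visit 11 (Extension Day 85, protocol Table 5): 85 − 1 = 84 days = 12 weeks after. With the ±7-day window this is 77 to 91 days.

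The two values are equally near. The literal rule takes Visit 11, which lies outside the Treatment Phase, and passes over Visit 7, which lies inside it. Protocol 9.1.3 allows dose adjustment in the Extension, so the later value may also be at another dose. Carrying the last observation forward would select Visit 7, so the LOCF label does not describe the rule.

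**5. Entire-study end point.** The rule asks for a value on or after the last disposition date, while 8.1 excludes Follow-up Phase values for these variables. The SAP does not say how an early discontinuation visit held after the last dose is classified.

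**The case against.** **On-treatment changes are not absent from every table.** A reader might infer that they are, and the documents do not support that. Protocol 9.5.1.5.1 makes a QTcF above 450 ms with a rise of more than 60 ms an adverse event, and the investigator may report any other ECG abnormality. SAP 5.6.2 tabulates TEAEs by dose, by 3-month period, and by whether they led to dose reduction, interruption or discontinuation. It also has a cardiac and ECG category of special interest. This stands. It does not reach values never reported as adverse events: a subject who meets only one of the two QTcF conditions depends on the investigator's judgement, and no numeric threshold is given for vital signs or weight.

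**The change is disclosed.** Protocol 9.7.1 leaves analytical detail to the SAP, and SAP section 7 lists the move to end of treatment. A charge of silent departure would be wrong for vital signs and ECG interpretation. What remains is the missing reason, the leftover by-visit references in 5.6, and the synopsis's ECG-parameter summary, which section 7 does not mention.

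**The late value is normally on drug.** A reader might infer that end-of-treatment values come from after perampanel was stopped. Section 8.1 keeps Follow-up values out, so a late Treatment Phase value would usually come from the Extension, on perampanel.

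**The rule may be meant more narrowly.** The phrase "the closest value measured on or post to the last disposition date in the Treatment Phase" could be read as confining the value, and not only the date, to the Treatment Phase. The reference to adequate data could also let a remote value be rejected. But nothing in a period follows the date on which it ended, so the narrow reading leaves the allowance for later values with no function. Adequate is not defined.

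**Conclusion.** The point holds in two parts.

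First, measured vital signs and ECG interpretation are tabulated at two end points, Treatment Phase and entire study, and nowhere between. For a 4 mg completer, two of three scheduled Treatment Phase assessments reach no table unless they gave rise to an adverse event. The SAP is also inconsistent with itself about by-visit tables, and that needs correcting whichever design is preferred.

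Second, the end-of-treatment rule as written has no upper limit and can put an Extension value, about 12 weeks late, into the Treatment Phase table. The example assumes a missing Visit 9 value, no unscheduled value and an Extension that starts at Visit 9. The documents give no basis for saying how often that would occur.

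A reader might add all the 4 mg and 8 mg visits to reach a larger denominator. That is not supported: a seizure ends 4 mg Maintenance before the move to 8 mg, so Visit 9 and the 8 mg visits would not normally occur in one subject.

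Neither part touches the primary efficacy analysis or the adverse event tables.

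**What to change.** 1. In SAP 8.1 and 8.3, define end of treatment as the last value belonging to the period, up to the disposition date plus the protocol's 7-day visit window. If there is none, use the last earlier on-treatment value in that period, and never a value from a later phase. Drop or correct the LOCF label, and state how an early discontinuation visit after the last dose is classified.
2. Choose one of two routes for coverage:
   - restore the by-visit vital-sign and ECG tables and write the visit windows into 8.3; or
   - delete the by-visit references in 5.6 and add a worst on-treatment ECG interpretation shift table, with counts of subjects with QTcF above 450 ms and with a rise of more than 60 ms.
3. Give a reason in section 7 for whatever remains changed from the protocol, including the synopsis's ECG-parameter summary.

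The QTcF counts go beyond protocol 9.7.1.8.5, which plans only interpretation shifts, but they use thresholds already in protocol 9.5.1.5.1. All the data are already collected. The cost is SAP wording and a few more tables to program and review.
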